5.4 General Concomitant Medication and Supportive Care Guidelines

General Supportive Care

Patients should receive full supportive care, including transfusions of blood and blood products, antibiotics, hematopoietic growth factors, analgesics, and antiemetics when appropriate.

Tumor Lysis Syndrome Prophylaxis

Tumor lysis syndrome (TLS), characterized by hyperkalemia, hyperuricemia, and hyperphosphatemia resulting from the rapid release of potassium, uric acid, and phosphate, has been reported in patients with CLL initiating venetoclax. There is a modest risk of TLS in patients treated with obinutuzumab, and as such it is recommended that patients receive allopurinol prior to starting on obinutuzumab. The risk of TLS on this study is highest during the first cycle of venetoclax combination therapy. It is strongly recommended that allopurinol 300mg PO daily begin 3 days before the initiation of venetoclax on cycle 4 day 1, and allopurinol should continue through the end of the first cycle of triple combination therapy. Patients with an allopurinol allergy should receive alternative TLS prophylaxis (e.g. febuxostat) if possible. In addition to pharmacologic TLS prophylaxis, all patients should be instructed to maintain adequate hydration and maintain urinary output as an additional measure to reduce the risk of TLS. Based on clinical and laboratory parameters, TLS prophylaxis may be continued or restarted as needed at the investigator's discretion. All patients meeting criteria of laboratory TLS or clinical TLS according to the Cairo-Bishop definition of TLS (Appendix D) should receive vigorous intravenous hydration and should be considered for rasburicase therapy as needed to reduce hyperuricemia, until correction of electrolyte abnormalities. See section 6.1, dose modification table, for additional instructions.

Hepatitis B Monitoring and Prophylaxis

Testing for hepatitis B surface antigen (HBsAg) and hepatitis B core antibody (HBcAb) is required for all subjects at the time of enrollment. Subjects who are positive for either HBsAg and/or HBcAb must also be tested for serum HBV DNA. Subjects who are positive for HBV DNA are excluded from the study. Subjects who are negative for HBV DNA but positive for

either HBsAg or HBcAb must receive pharmacologic prophylaxis to prevent HBV reactivation. Entecavir is the preferred agent for pharmacologic prophylaxis. Use of an agent other than entecavir must be discussed with the principal investigator. Prophylaxis should be administered for as long as the subject is receiving a study medication or for up to 12 months after the last dose of obinutuzumab, whichever is longer. HBV DNA should be monitored every three months while a patient is receiving pharmacologic prophylaxis. If the HBV DNA level becomes detectable, all study medications should be discontinued and infectious disease consultation should be obtained. If a subject who meets criteria for prophylaxis is not willing or able to receive prophylaxis, then he/she will be excluded from the study.

Growth Factor Support

White blood cell growth factor support with Neulasta, Neupogen, or tbo-filgrastim (Granix) will be administered at the discretion of the treating investigators with dosing as per standard of care. Neulasta, Neupogen, and Granix will be from commercial supply.

Prophylactic Antibiotics

Prophylaxis for *Pneumocystis jiroveci* pneumonia (PCP) with trimethoprim/sulfamethoxazole (typically given as one single-strength tablet daily) or equivalent is mandatory for all patients. Anti-herpetic viral prophylaxis with acyclovir (typically given as 400mg po tid) or equivalent is mandatory for all patients.

Intravenous Immunoglobulin

Immunoglobulin replacement with intravenous immunoglobulin (IvIg) therapy is permitted for patients who, at the discretion of the investigator, require IvIg for primary prophylactic or secondary prevention of infection.

Moderate or Strong CYP3A Modulators

Minor CYP3A4 inducers or inhibitors (e.g. amlodipine) are allowed without any dose changes to the study drugs. Patients who require treatment with strong CYP3A inhibitors or inducers (partial list in Appendix F) are excluded from enrollment in the study. However, if treatment with strong CYP3A inhibitors becomes necessary while subjects are on study treatment, dosing of venetoclax and acalabrutinib should be managed as detailed in Table 4 below. Of note, venetoclax should held if treatment with strong CYP3A inhibitors or inducers is required during the ramp-up phase of drug administration. Dosing of acalabrutinib should be interrupted while the subject is on the strong CYP3A inhibitor, as detailed in Table 4 below. Three days after discontinuation of the strong CYP3A inhibitor, resume acalabrutinib and resume or increase venetoclax to the dose that was used prior to initiating the CYP3A inhibitor.

If treatment with moderate CYP3A inhibitors (see partial list in Appendix F) is required while subjects are on study, dosing of venetoclax and acalabrutinib should be reduced as detailed in Table 4 below. Three days after discontinuation of the moderate CYP3A inhibitor, increase acalabrutinib and venetoclax to the doses that were used prior to initiating the CYP3A inhibitor.

If treatment with strong or moderate CYP3A inducers is required while the subject is on study, doses of venetoclax and acalabrutinib should be modified as detailed in Table 4. Three days after discontinuation of the strong CYP3A inducer, reduce acalabrutinib and resume venetoclax at the dose that was used prior to initiating the CYP3A inhibitor.

Dosing modifications of acalabrutinib and venetoclax do not need to be made if patients are receiving inhibitors or inducers of other CYP450 enzymes.

Table 4: Dosing Modifications in the Setting of CYP3A Modulators and P-gp Inhibitors

Medication Class	Initiation and Ramp-	Steady Daily Dose of	Steady Daily Dose of
	Up Phase of	Venetoclax (after	Acalabrutinib
	Venetoclax	ramp up phase)	
Strong CYP3A Inhibitor	Contraindicated, hold	Reduce venetoclax	Interrupt acalabrutinib
	venetoclax	dose by 75% (e.g.	dosing
		100mg daily)	
Moderate CYP3A	Reduce venetoclax	Reduce venetoclax	Reduce acalabrutinib
inhibitor	dose by 50%	dose by 50% (e.g.	dose by 50% (e.g.
		200mg daily)	100mg once daily)
Strong CYP3A Inducer	Contraindicated, hold	Contraindicated, hold	Double acalabrutinib
	venetoclax	venetoclax	dose (e.g. 200mg twice
			daily)
Moderate CYP3A	Contraindicated, hold	Contraindicated, hold	Maintain acalabrutinib
Inducer	venetoclax	venetoclax	dose (e.g. 100mg twice
			daily)
P-gp Inhibitors or P-gp	Contraindicated, hold	Reduce venetoclax	No change to dose
Substrates of Narrow	venetoclax	dose by 50% (e.g.	
Therapeutic Index		200mg daily). Take	
		inhibitor at least 6	
		hours before	
		venetoclax.	

P-gp Inhibitors or P-gp Substrates of Narrow Therapeutic Index

Patients who require treatment with P-gp inhibitors or P-gp substrates of narrow therapeutic index (partial list in Appendix F) are excluded from enrollment in the study. However, if treatment with these drugs becomes necessary while subjects are on study treatment, dosing of venetoclax should be managed as detailed in Table 4 above. If a narrow therapeutic index P-gp substrate must be used, it should be taken at least 6 hours before venetoclax. Resume the venetoclax dose that was used prior to initiating the P-gp inhibitor 3 days after discontinuation of the inhibitor.

Drug-Drug Interactions

Because there is a potential for interaction of acalabrutinib and venetoclax with other concomitantly administered drugs through the cytochrome P450 system, the case report form

must capture the concurrent use of all other drugs, over-the-counter medications, or alternative therapies. If there are known drug-drug interactions between the study drug(s) and other medications that the patient is taking, dose reductions of the study drug(s) may occur at the discretion of the treating investigator.

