Acalabrutinib will be administered orally twice daily during each 28-day cycle. Obintuzumab will be given intravenously at the standard dosing of six monthly cycles (with loading doses administered weekly during the first month). Venetoclax will be given orally daily with ramp-up stepwise dosing during the first month of therapy until the standard dose is achieved. After the six cycles of obinutuzumab are completed, venetoclax and acalabrutinib will continue as combination therapy until cycles 15, 24, or indefinitely (as outlined in Study Overview, above).

Definition of Unexpected Toxicities

Unexpected toxicities would include the following events that occur during AVO treatment, unless they are clearly due to extraneous causes: any grade 3 or higher clinically significant nonhematologic toxicities related to study treatment, grade 4 or higher infusion reaction, grade 4 or higher tumor lysis syndrome, grade 4 or higher infection, and grade 4 or higher neutropenia. Grade 3 or 4 drug-related toxicities occurring after the first cycle of treatment will be discussed with the Principal Investigator and will be considered in decisions regarding the recommended dose for future studies. The IWCLL Grading Scale for Hematologic Toxicity in CLL Studies will be used to grade hematologic toxicities and the National Cancer Institute Common Terminology Criteria for Adverse Events (NCI-CTCAE) Version 5.0 will be used to grade non-hematologic toxicities during the trial unless otherwise specified.

Study Drug

Acalabrutinib is administered orally twice daily as a tablet formulation. The acalabrutinib drug product is supplied as 100mg tablets. Obinutuzumab is administered intravenously. Venetoclax is administered orally daily as a tablet formulation, with tablet strengths varying based on dosing.

Key Eligibility Criteria (for complete eligibility criteria, see section 3.1)

Inclusion Criteria

- Subjects must have CLL, SLL, or B-prolymphocytic leukemia (B-PLL)
- Subjects must have *TP53*-aberrant disease, defined as the detection of del(17p) and/or the presence of a *TP53* mutation
- Participants must have measurable disease (lymphocytosis > 5,000 / μ l, or palpable or CT measurable lymphadenopathy \geq 1.5 cm, or bone marrow involvement \geq 30%).

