8.1 Venetoclax

Description

Venetoclax (ABT-199/GDC-0199) is a novel, orally bioavailable, small-molecule Bcl-2 family inhibitor in the biarylacylsulfonamide chemical class. Venetoclax binds with high affinity ($K_i < 0.010 \text{ nM}$) to antiapoptotic protein Bcl-2 and with lower affinity to other antiapoptotic Bcl-2 family proteins, like Bcl- X_L and Bcl-w (> 4,800-fold and > 24,500-fold lower affinity than to Bcl-2, respectively).

In vitro studies have shown that venetoclax is metabolized primarily by CYP3A4. Interaction of venetoclax with co-administered CYP3A inhibitors or inducers may cause an increase or decrease in the exposure of venetoclax. In vivo, venetoclax was also demonstrated to be metabolized by CYP3A4. Venetoclax is also substrate for P-glycoprotein (P-gp) and breast cancer resistance protein (BCRP) transporters. Renal contribution to the elimination of venetoclax is negligible, with < 0.1% of the dose being recovered in urine. Based on in vitro results, venetoclax was a P-gp, BCRP, and OATP1B1 inhibitor. It was not a potent in vitro inhibitor of CYP3A4, CYP1A2, CYP2B6, or CYP2D6 (IC50 > 30 μ M); and it did not induce CYP3A4 or CYP1A2 at concentrations up to 10 μ M. Venetoclax is also not predicted to cause inhibition of CYP2C19, CYP2C8, CYP2C9, and UGT1A1 at clinically relevant concentrations. It is not an inhibitor of UGT1A4, UGT1A6, UGT1A9 and UGT2B7. Following coadministration of a single dose of venetoclax with warfarin, R- and S-warfarin C_{max} and AUC_{∞} increased by approximately 18% to 28%. Relatively low variability was observed in warfarin pharmacokinetics.

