The venetoclax formulation currently used in clinical studies is a tablet formulation with strengths of 10, 50, and 100 mg. The tablet formulation was orally administered after a low-fat meal. Food increased the bioavailability of venetoclax by 3- to 5-fold. Preliminary pharmacokinetic results indicated that the absorption of venetoclax after the oral dosing was relatively slow. Venetoclax plasma concentrations peaked at approximately 5 to 8 hours after dosing. The mean harmonic terminal phase half-life from 17 to 41 hours and the mean oral clearance was approximately 13 L/hr after a single dose. Preliminary data did not suggest apparent pharmacokinetics differences among subjects with CLL/SLL, NHL, Multiple Myeloma, Acute Myeloid Leukemia, or systemic lupus erythematosus. The combined data from subjects with CLL/SLL and NHL suggested that venetoclax exposure was approximately dose proportional across the 150 to 800 mg dose levels at steady state. Additional information about venetoclax is available in the package insert.

Form

Venetoclax tablets are film coated and are available in strengths of 10 mg, 50 mg, or 100 mg.

Venetoclax will be packaged in high density polyethylene (HDPE) plastic bottles. Each bottle will be labeled per local regulatory requirements. Labels must remain affixed to the bottle.

Storage and Stability

Venetoclax must be stored at 15° to 25°C (59° to 77°F). The investigational products are for investigational use only and are to be used only within the context of this study. The study drug supplied for this study must be maintained under adequate security and stored under the conditions specified on the label until dispensed for subject use or returned to Genentech. Labels must remain attached to the containers.

If a temperature excursion is experienced at any site beyond the stated storage parameters, the site must report the excursion and associated details to the lead site project manager as soon as feasible.

Compatibility

N/A

Handling

Qualified personnel, familiar with procedures that minimize undue exposure to themselves and the environment, should undertake the preparation, handling, and safe disposal of the chemotherapeutic agent in a self-contained and protective environment.

Availability

Venetoclax is provided by Genentech directly to the study site.

Preparation

N/A

Administration

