Oral. Patients should take venetoclax tablets with a meal and water at approximately the same time each day. Venetoclax tablets should be swallowed whole and not chewed, crushed, or broken prior to swallowing.

If vomiting occurs within 15 minutes after taking venetoclax and all expelled tablets are still intact, another dose may be given. Otherwise, no replacement dose is to be given. In cases where a dose of venetoclax is missed or forgotten, the patient should take the dose as soon as possible and ensure that the minimal interval between the current dose and the next dose is at least 16 hours in order to avoid excessive drug accumulation after the next dose.

Any overdose or incorrect administration of study drug should be noted in the medical chart.

Adverse events associated with an overdose or incorrect administration of study drug should be reported.

Ordering

Venetoclax will be ordered directly from Genentech, who will ship drug directly to the DF/HCC study sites with an order form provided at the time of study activation.

External (Non-DF/HCC) investigative sites will be provided with a study specific drug order form by the lead site project manager once all necessary documents are collected, and the site is otherwise approved to enroll participants on the study.

The drug will be provided at no cost to the participant.

Accountability

The investigator, or a responsible party designated by the investigator, should maintain a careful record of the inventory and disposition of the agent using a drug accountability form.

Destruction and Return

If pre-arranged between Genentech and the site, destruction of used and unused study drug may be performed at the site. Empty containers will be destroyed at the site.

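### Section 5.4 and Table 4 contain interaction rules that cannot be carried out with the supplied tablets or do not match each other, so sites could handle the same patient differently

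*Combined protocol and SAP*

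**What the plan says.** **Percentage reductions.** Table 4 (Section 5.4) gives venetoclax and acalabrutinib changes by class of interacting drug. For a moderate CYP3A inhibitor, venetoclax is cut by 50% both in ramp-up and afterwards, and acalabrutinib is cut by 50%. For a strong CYP3A inhibitor after ramp-up, venetoclax is cut by 75%. The printed examples all start from the full doses.

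**Tablets.** Section 8.1 (Venetoclax) states: "Venetoclax tablets are film coated and are available in strengths of 10 mg, 50 mg, or 100 mg", and "Venetoclax tablets should be swallowed whole and not chewed, crushed, or broken prior to swallowing". The synopsis states: "The acalabrutinib drug product is supplied as 100mg tablets". Sections 5.3 and 8.1 (Acalabrutinib) require those tablets to be swallowed intact.

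**P-gp drugs.** One row of Table 4 covers both P-gp inhibitors and narrow-therapeutic-index P-gp substrates: venetoclax is held in ramp-up and halved afterwards. That row places the "inhibitor at least 6" hours before venetoclax. The text beneath sends both classes to Table 4 for the venetoclax dose and then adds: "If a narrow therapeutic index P-gp substrate must be used, it should be taken at least 6 hours before venetoclax". The only return instruction is: "Resume the venetoclax dose that was used prior to initiating the P-gp inhibitor 3 days after discontinuation of the inhibitor".

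**Inducers.** The text sends strong and moderate CYP3A inducers to Table 4, which marks venetoclax as contraindicated and held for both. The restart sentence sets a three-day wait and reads, in part: "discontinuation of the strong CYP3A inducer, reduce acalabrutinib and resume venetoclax at the dose that was used prior to initiating the CYP3A inhibitor". Appendix F lists moderate inducers under a cautionary heading.

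**The concern.** A dosing table in a protocol should lead two sites with the same patient to the same action. Here it may not, in three places.

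- A percentage that falls between tablet sizes leaves the site to round, and the protocol gives no rounding rule. This matters most in ramp-up. The venetoclax adverse event list in Section 7.1 says that CYP3A inhibitors, moderate ones included, raise venetoclax exposure and may raise the risk of tumor lysis syndrome at initiation and during ramp-up. Section 3.1 excludes patients who need strong CYP3A inhibitors but does not exclude moderate ones, so the case can arise in an eligible patient on the standard schedule.
- For P-gp drugs, table and text attach the spacing to different classes, and a patient whose venetoclax was changed for a substrate has no stated return to the earlier dose.
- For inducers, the restart sentence points to a drug the patient need not have taken. A patient held for a moderate inducer has no restart line, and Appendix F describes that class less strictly than Table 4.

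Section 2.4 extends the study to community sites, which makes a single readable rule more important. What is at stake is consistent study-drug exposure and handling, not the statistical design.

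**Working it through.** **1. Can the percentages be dispensed?**

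Inputs: tablet strengths and the whole-tablet rule (Sections 5.3 and 8.1, synopsis); ramp-up steps 20, 50, 100, 200 and 400 mg (Section 5.3); reduced venetoclax levels (Table 5); reduced acalabrutinib level, 100 mg once daily (Table 11).

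Table 4's own examples reproduce:

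- Venetoclax: 400 × 0.25 = 100 mg and 400 × 0.5 = 200 mg.
- Acalabrutinib: 200 mg per day × 0.5 = 100 mg per day; doubled, 200 mg twice daily.

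All of these can be made.

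Whole 10, 50 and 100 mg tablets give only multiples of 10 mg. Applying the same percentages to every venetoclax level:

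| Current dose (mg) | Where it occurs | After 50% cut | Can be made? | After 75% cut | Can be made? |
|---|---|---|---|---|---|
| 400 | ramp-up, steady | 200 | yes | 100 | yes |
| 300 | Table 5 | 150 | yes | 75 | **no** |
| 200 | ramp-up, Table 5 | 100 | yes | 50 | yes |
| 100 | ramp-up, Table 5 | 50 | yes | 25 | **no** |
| 50 | ramp-up, Table 5 | 25 | **no** | 12.5 | **no** |
| 20 | ramp-up, Table 5 | 10 | yes | 5 | **no** |
| 10 | Table 5 | 5 | **no** | 2.5 | **no** |

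The 75% cut applies only after ramp-up, so its failures need an earlier dose reduction. The 50% cut at 50 mg needs none: it follows from a moderate CYP3A inhibitor during cycle 4 days 2-7. It could recur if ramp-up is repeated at retreatment (Section 5.1 and the retreatment calendar in Section 10).

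The multiples of 10 mg on either side of 25 mg are 20 and 30 mg. They correspond to cuts of 1 − 20/50 = 60% and 1 − 30/50 = 40%. These figures show the spread that a site's rounding could produce; neither is put forward as an answer.

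Acalabrutinib at 100 mg once daily, cut by 50%, gives 50 mg per day. Whole 100 mg tablets cannot make that as a daily dose.

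**2. Does each class have a way back?**

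Table 4 has five rows. Counting the two P-gp classes separately gives six:

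| Class | Venetoclax in ramp-up | Venetoclax afterwards | Return line in Section 5.4 |
|---|---|---|---|
| Strong CYP3A inhibitor | hold | cut 75% | yes, 3 days |
| Moderate CYP3A inhibitor | cut 50% | cut 50% | yes, 3 days |
| Strong CYP3A inducer | hold | hold | yes, 3 days, but tied to the dose before an inhibitor |
| Moderate CYP3A inducer | hold | hold | none |
| P-gp inhibitor | hold | cut 50% | yes, 3 days |
| Narrow-index P-gp substrate | hold | cut 50% | none |

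Two of the six have no return line, and a third refers to the wrong class of drug.

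**3. Do the places agree?**

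- Spacing: Table 4 names the inhibitor; the text names the substrate.
- Venetoclax dose for P-gp drugs: table and text agree, because the text defers to the table.
- Status of moderate inducers: contraindicated in Table 4, cautionary in Appendix F.

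**The case against.** The strongest reply is that most of this is loose drafting.

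- **P-gp timing.** A patient on an inhibitor can follow the table and a patient on a substrate can follow the text, so both statements can be obeyed. That stands: it is a mismatch, not a pair of opposed instructions. A site still cannot tell whether the spacing is meant for one class or both.
- **P-gp dose.** A reader might infer that the mismatch decides whether venetoclax runs at half dose. It does not, since the text sends both classes to Table 4. A reader might also infer a large loss of planned venetoclax by the cycle 15 endpoint in substrate patients. That would require the substrate to stop almost at once and the dose never to be restored. If the substrate continues, half dose is what Table 4 prescribes.
- **Pharmacology.** Section 8.1 says "Based on in vitro results, venetoclax was a P-gp, BCRP, and OATP1B1 inhibitor", and a reader might infer that substrates do not belong in the inhibitor's row. Whether the two classes should share a venetoclax rule is a clinical judgement for the sponsor, not a contradiction in the documents.
- **Inducers.** The sentence opens with the inducer, so the later reference to an inhibitor is evidently a wrong word. That stands, but the missing moderate-inducer line and the Appendix F label remain.
- **Tablets.** Only one failure lies on the standard schedule; the others need an interaction on top of an earlier reduction. That stands. Tumor lysis laboratory checks around each first ramp-up dose limit the consequence, and Section 5.4 leaves interaction-related reductions to investigator discretion. Neither makes 25 mg dispensable, and discretion permits the variation at issue.
- **Frequency.** Patients who need strong CYP3A modulators or P-gp drugs are excluded at enrolment, so those cases arise only incidentally.

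**Conclusion.** The point holds as a set of gaps and mismatches, one of which makes a stated rule impossible to carry out. Halving the 50 mg ramp-up step gives a dose that the supplied tablets cannot make: one of five steps, covering six days of cycle 4. The reduced-dose failures are real but less frequent. Two of six interacting classes lack a return-to-dose line, one restart sentence names the wrong class, the P-gp spacing is attached to different classes in table and text, and the moderate-inducer label differs between Table 4 and Appendix F.

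This rests on the tablet strengths and whole-tablet rules as printed. The documents support saying that sites could act differently; a reader might infer that they will, but nothing shows that they have or must. The number of patients affected is unknown. The sample size, power and type I error do not depend on any of this. The matter should be corrected, but it does not threaten the primary analysis.

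**What to change.** In one amendment:

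- Reconcile Table 4 with the Section 5.4 text on which P-gp class, or classes, the 6-hour spacing applies to.
- Reconcile Table 4 with Appendix F on the status of moderate CYP3A inducers.
- Correct the inducer restart sentence so that it refers to the class it is about.
- State a return-to-dose rule for every class for which Table 4 changes venetoclax, including moderate inducers and narrow-index P-gp substrates.
- Reconcile Table 4's percentages with the supplied tablet strengths at each ramp-up step, each Table 5 level and the reduced acalabrutinib level in Table 11.

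The sponsor and the drug suppliers decide every value and rule; none is proposed here. The cost is one amendment to Section 5.4, Table 4 and Appendix F plus a memo to sites, with no new procedures or patients.
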